8.7. PROCEDURES FOR COHORT 2 (HEALTH PROFESSIONALS)⁶

Interviews with up to 15 health professionals will each last 30 minutes. Topic guides will focus on understanding perceptions of the EDGE system e.g. usability and level of integration within existing clinical pathways.

9.2. COHORT 2 (HEALTH PROFESSIONALS)

It will be verbally explained, as well as clearly stated in the participant information leaflet, that participants are free to withdraw from the study at any time for any reason. Health professionals wishing to withdraw from the study may do so before or during the interview. It will be explained when consent is taken that should they wish to withdraw after the interview has taken place it may not be possible to delete the data they have provided because the audio-file transcripts will be de-identified.

10. DEFINITION OF END OF STUDY

The end of study is the point at which all the data has been entered and queries resolved after the 5 year follow up period.

11. PATIENT AND DATA SAFETY

11.1. POTENTIAL RISKS AND BURDENS TO PARTICIPANTS

It is unlikely that the use of the tablet computer will lead to any harm. However, we will monitor the system and identify any unanticipated safety issues. In addition to using the tablet computer, participants will have multiple research contacts; contacted within 10 working days of discharge and within ~4-6 weeks, and after ~12, ~24 and ~52 weeks following the date of consent.

It is anticipated that by monitoring their COPD symptoms (e.g. cough and phlegm) more closely, patients may feel more anxious about their condition. Educational components contained within the tablet computer will be incorporated to assist in COPD self-management. In addition, patients will have access to the clinical research team whilst taking part.

Taking part in an interview may lead to patients talking about sensitive or upsetting issues. Although this research does not focus on a sensitive topic, some patients may experience emotional distress. If this does occur, the researcher will allow the patient to recover and then proceed when the participant is willing and able to. The researcher would also encourage the patient to inform their carer and/or healthcare professional, if this is appropriate. As the research involves patients living with a respiratory

condition, patients may experience breathlessness when talking for long periods. If this situation arises, the researcher will allow the patient time to recover their breathing and only continue if/when the patient feels able to. The researcher will also encourage the patient to contact their respiratory nurse if their breathlessness is worse than normal.

It will be explained before the start of the interview that everything said during the meeting will remain confidential and will not be disclosed beyond the research team unless there is an overriding legal or public interest in disclosure to an appropriate authority, for example a safeguarding duty.

Members of the non-clinical research team at the University of Oxford will liaise directly with NHS Digital to obtain data pertaining to patient mortality (e.g. date and cause of; originally noted by the Office of National Statistics or 'ONS') and hospital episode statistics (e.g. hospital admissions, A&E attendances and outpatient appointments; originally noted by the Hospital Episodes Statistics or 'HES') over 5 years following date of discharge from hospital. This will only be conducted for patients who have consented to take part in EDGE2. NHS Digital will request minimal information (e.g. NHS identifier and date of birth) to extract relevant data.

Amalgamation of datasets is classified as 'high risk' by the Information Commissioners Office because a breach in data security could result in exposure of an increased amount of personal data than a single dataset. To minimise risk only data that is required to answer the research objectives will be collected and risk will be sufficiently mitigated through using a study ID number to anonymise the incoming data. In accordance with information governance policy, datasets will be securely stored on a server behind the NHS firewall and/or on a restricted local sever managed by the University of Oxford. All data will only be accessible to authorised members of the study team. Patient identifiers will never be stored with any study data and any published/reported results will be entirely anonymous.

12. STATISTICS AND ANALYSIS

12.1. DESCRIPTION OF STATISTICAL METHODS FOR OUTCOME MEASURES

A combination of quantitative and qualitative data analysis will be conducted.

12.1.1. QUANTITATIVE DATA ANALYSIS

Descriptive statistics will be used to summarise the baseline characteristics of patients. The primary outcome will involve descriptive statistics in the form of frequency, spread of data (mean and standard deviation or median and interquartile range), proportion (%) and/or range of values (confidence intervals). It will also involve exploratory analysis to look at the number of days data was received compared with the expected number.

Statistical methods to analyse the data will include repeated measures analysis of (co)variance and linear regression for continuous variables. Effects will be assessed by analysis of sub-groups defined by smoking status, hospital admission history, COPD severity (e.g. FEV₁). Covariates will include weather conditions (e.g. temperature) and patient demographics (e.g. age or sex). Further additional exploratory analysis will look at number of days of tablet exposure (and use) whilst at hospital, the number of days data was received from the tablet compared with the expected number, as well as general tablet computer use. Additional exploratory use of data: We will add in iterations of predictive algorithms to the system used

12.1.2. QUALITATIVE DATA ANALYSIS

in EDGE2, record the findings, and then analyse their performance in samples.

The interview data with patients and health professionals will be audio-recorded, transcribed and analysed using a reflexive thematic analysis approach. Transcription will be completed by an experienced transcriber, with any personally identifiable information removed and replaced. This data will be imported into software (such as NVivo12) to facilitate storage, organisation and analysis.

12.2. THE NUMBER OF PARTICIPANTS

No sample size calculation has been completed for this cohort study because the primary outcome is to determine the feasibility of integrating hospital data with ad-hoc data collected at home. Up to 200 patients (100 as a minimum) has been drawn up as a target sample size so we can recruit a sizeable sample of patients which will allow the researchers to identify how data linkage fares between patients. It is anticipated that up to 30 patients living with COPD will take part in interviews and up to 15 health professionals will participate in interviews.

13. DATA MANAGEMENT

13.1. SOURCE DATA

Source data will be supplied directly by patients for several Case Report Forms (CRFs), including but not limited to the baseline questionnaire, follow up questionnaire and patient contact details form. Alongside this, source documents (including but not limited to secondary care records/notes and NHS Digital datasets) will be used to obtain relevant data (e.g. admissions to hospital and mortality) to complete the other CRFs (e.g. hospital record extraction form). Data will also be supplied by digital devices (including the wrist-worn activity monitor and pulse oximeter) worn/used by the participants. All data and associated documents will be stored according to information governance guidelines.

13.2. ACCESS TO DATA

Direct access will be granted to authorised representatives from the Sponsor and host institution for monitoring and/or audit of the study to ensure compliance with regulations. Access to the data collected from participants via the tablet computer will be given to CI-approved members of the CRT holding a contract with Oxford University Hospitals NHS Trust, to provide greater insight into their patient's health over time. This may be beneficial during the remote management of CRT patients.

13.3. DATA RECORDING AND RECORD KEEPING

Each participant will be assigned a study identity code number for use on CRFs, other study documents and electronic databases. CRFs in a physical form will be treated as confidential documents and held in a secure location (locked cabinet/draw in a secure authorised-personnel only building) and only accessible by research personnel in accordance with regulation. CRFs in an electronic form will be treated as confidential documents and held securely on password protected University or NHS computers. Upon entry into the CRF, data will be manually entered into the trial database and exported for analysis. CRFs will be restricted to personnel approved by the Chief Investigator and recorded on the delegation of duties log in the trial master file.

The investigator will ensure the creation of a separate confidential record of patients' identifiable information (e.g. names, dates of birth and local hospital number or NHS number) to allow identification of participants enrolled in the study, in accordance with regulatory requirements and for follow-up (as necessary). Inherently identifiable data (e.g. consent forms and transfer forms) will be held separately from de-identified data.

All qualitative data will be stored securely on a password protected University computer, separately from the quantitative trial database. Audio recordings from the interviews will be shared electronically (via a password protected, secure website) to transcribe the files verbatim. Transcripts will be sent from the transcriber directly to the researcher electronically. Audio recordings will be deleted by the transcriber as soon as they have completed transcription of each file. The research team will keep an electronic copy of the audio recordings until all transcription, data collection and analysis are complete. Analysis of the qualitative data will make use of coded names where the name of the individual taking part in the interview is mentioned.

Mortality (cause and date of) and hospital episode statistics obtained via NHS Digital will be kept on University of Oxford servers.

The Chief Investigator will maintain all records and documents regarding the conduct of the study. These will be retained for 20 years or for longer, as required. If the responsible investigator is no longer able to maintain the study records, a second person shall be nominated who will take over this responsibility.

The trial master file and study documents held by the Chief Investigator shall be securely archived at secure archive facilities at the University of Oxford. This archive shall include all study databases and associated encryption codes (as appropriate).

14. QUALITY ASSURANCE PROCEDURES

The study may be monitored, or audited in accordance with the current approved protocol, GCP, relevant regulations and standard operating procedures. In an effort to abide by quality assurance principles, trial conduct will be subject to the audit of the trial master file for inclusion of essential documents including: permissions to conduct the trial, CVs of trial staff and training received, local document control procedures, consent procedures and recruitment logs, adherence to procedures defined in the protocol (e.g. inclusion/exclusion criteria), adverse event recording and reporting and accountability of trial materials (as appropriate).

Monitoring of trial data shall include confirmation of informed consent, source data verification, data storage and data transfer procedures, as well as back-up and disaster recovery of any local databases and validation of data manipulation. Entries on CRFs may be verified by inspection against the source data. The trial database will also be checked for any potential discrepancies/errors during the data entry process. Any corrections will be noted by the investigators.

15. ETHICAL AND REGULATORY CONSIDERATIONS

15.1. DECLARATION OF HELSINKI

The Investigator will ensure that this study is conducted in accordance with the principles of the Declaration of Helsinki.

15.2. GUIDELINES FOR GOOD CLINICAL PRACTICE

The Investigator will ensure that this study is conducted in accordance with relevant regulations and with Good Clinical Practice.

15.3. APPROVALS

The protocol, informed consent form, participant information leaflet and data collection questionnaires will be submitted to an appropriate Research Ethics Committee (REC), and HRA for written approval. The Investigator will submit and, where necessary, obtain approval from the above parties for all substantial amendments to the original approved documents.

15.4. REPORTING

The Chief Investigator shall submit once a year throughout the study, or on request, an Annual Progress report to the REC Committee, HRA (where required) host organisation and Sponsor. In addition, an End of Study notification and final report will be submitted to the same parties.

15.5. PARTICIPANT CONFIDENTIALITY

The study staff will ensure that the participants' (patients and health professionals) anonymity is maintained. The participants will be identified only by a participant ID number on all study documents and any electronic database (except the tablet computer web interface that will also include the participant's NHS number as a secondary identifier for clinical purposes. These data are hosted on NHS servers), except for the consent form and other inherently identifiable forms used to gather participant contact details (e.g. the Study Reply Form), and a separate confidential record will be created that encloses participants' names, dates of birth, home addresses and study identity code number. The latter will be an encrypted database kept separately from all other study data and will kept only long enough to allow for patient follow up. All documents will be stored securely and only accessible by study staff and authorised personnel, determined by the Chief Investigator. The study will comply with the General Data Protection Regulation 2018 and Data Protection Act 2018 which requires data to be de-identified/pseudo-anonymised as soon as it is practical to do so.

15.6. EXPENSES AND PARTICIPANT BENEFITS

Reasonable travel expenses for any visits additional to normal care will be reimbursed on production of receipts, or a mileage allowance provided as appropriate. Follow up contacts made by the research nurse will be made to the patient whilst at home (if they feel comfortable with this arrangement) in an effort to limit the opportunity for patient expense and to help minimise patient burden.

15.7. TRIAL PARTICIPATION

All participants will continue to receive the standard care offered to all COPD patients by their usual care provider (respiratory nurse and/or GP). This will be made clear to potential participants in the participant information leaflets as well as explained verbally during the process of obtaining informed consent. It will also be made clear that the decision to participate or not (or provide consent to participate and subsequently wish to withdraw) will not in any way affect the standard of care and treatment usually received by these patients.

16. FINANCE AND INSURANCE

16.1. FUNDING

The study will be funded by the NIHR Oxford Biomedical Research Council under the Technology and Digital Health Stream and by the Engineering and Physical Sciences Research Council.

16.2. INSURANCE

The University has a specialist insurance policy in place which would operate in the event of any participant suffering harm as a result of their involvement in the research (Newline Underwriting Management Ltd, at Lloyd's of London). NHS indemnity operates in respect of the clinical treatment provided.

16.3. PUBLICATION POLICY

The Investigators will be involved in reviewing drafts of the manuscripts, abstracts, press releases and any other publications arising from the study. Authors will acknowledge that the study was funded by the NIHR Oxford Biomedical Research Centre and the Engineering and Physical Sciences Research Council.

17. DEVELOPMENT OF A NEW PRODUCT/ PROCESS OR THE GENERATION OF INTELLECTUAL PROPERTY

Ownership of IP generated by employees of the University vests in the University. The protection and exploitation of any new IP is managed by the University's technology transfer office, Oxford University Innovations.

18. FEEDBACK TO PARTICIPANTS

[figure not shown]
Participants will be informed of the trial results through an information sheet prepared for a lay audience made available on the department's website.

21. APPENDIX B: HOSPITAL DATA

The following example categories of data are held in the SEND/HAVEN databases*:

- 1. Electronic Patient Record database
- 2. Patient Administration System database
- 3. Vital signs database
- 4. Radiology database ("PACS")
- 5. Pathology ("LIMS") database (laboratory values including blood gases)
- 6. Theatre Management Systems databases.
- 7. The Trust's Data Warehouse
- 8. The Trust's Clinical Data Repository
- 9. Intensive Care Audit Database (ICNARC)
- 10. The Trust's Cardiac Arrest Audit Database
- 11. The Trust's blood transfusion database ("Bloodtrack")
- 12. The Trust's intensive care patient record database
- *We will only use data from patients who have consented.

[figure not shown]
22. APPENDIX C: SCHEDULE OF STUDY PROCEDURES FOR COHORT 1

For patients who give consent to take part whilst they are in hospital:

*Patient interviews (n=up to 20) will take place at the within ~4-week and ~24-week contact after hospital discharge (unless withdrawn, in which case it will take place at an ad-hoc timepoint) *Access to the tablet system will start from provision of consent but the 6 months will start from the point of hospital discharge

For patients who give consent to be contacted about taking part after discharge:

*Patient interviews (n=up to 20) will take place at the within ~6-week and ~24-week contact after hospital discharge (unless withdrawn, in which case it will take place at an ad-hoc timepoint)

*Access to the tablet system will start from provision of consent but the 6 months will start from the point of hospital discharge

23. APPENDIX D: PROCEDURES MATRIX

Procedures	During screening	At baseline (either in hospital or within ~6-weeks of discharge)	An ongoing procedure	At the within ~4- week assessment	At the ~12- week assessment	At the ~24- week assessment	At the ~52- week assessment	5 year passive follow up
Approach potentially eligible patients	x							
Conduct an eligibility assessment	x	x						
Obtain informed consent		X [prior to baseline if using verbal consent]	x [for health professionals and patients undertaking interview]					
Collect contact details		x	x [if details change]					
Collect medical history		x						
Ask patients to complete the questionnaires		x					x	
Linkage of patients' in- hospital data		x	x					
Access hospital records		x					x	
Ask patients to complete a physical function assessment (sit-to-stand test)		x [if feasible]		x	x	x	x	
Complete the process measure questionnaire (COPD care bundle)		х		x				
Provide tablet and monitoring		x						

devices to patients					
Collect tablet and monitoring devices from patients		x [if participant withdraws]		x	
Conduct patient interviews ⁷	x [if baseline occurs after discharge]	x [in the event a participant withdraws and consented to be contacted about interviews]		x	
Conduct health professional interviews		x			
Collection of data from NHS Digital					x

⁷ A subset of a further 10 patients will also be interviewed at ~18 and ~32 weeks

24. APPENDIX E: MEASUREMENTS MATRIX

	At baseline (either in hospital or within ~6- weeks of discharge)	At 4 weeks	At 12 weeks	At 24 weeks	At 52 weeks	Data accessed from hospital records	An ongoing measure (up until 5 year follow up)
PRIMA	RY OUTCOME	MEASURE	S				•
Linkage of hospital and tablet data	x						x
SECON	IDARY OUTCOM	ME MEASU	JRES		-		•
SGRQ-C	х				x		
EQ-5D-5L	х				x		
MGL scale	х				x		
Smoking status	х				х		
Self-efficacy	х				x		
Admissions to hospital	x [in preceding year]				x [any subsequent visits]	x	
Admissions to ICU	x [in preceding year]				x [any subsequent visits]	x	
Number of contacts with healthcare professionals	x [in preceding year]				x [any subsequent visits]		
Medication and oxygen therapy	x				x		
Physical function	x	х	х	х	x		
Costs of the digital intervention	x				x		
Death		х	х	х	х		х
COVID-19 Status	x	х	х	х	x		
Hospital episode statistics							х
SECON	IDARY PROCES		ES				
COPD care bundle	х	х					

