Secondary1. To determine the impact of the intervention.2. To link patient data obtained	 SGRQ-C (respiratory questionnaire for COPD) EQ-5D (quality of life) MGL scale (medication adherence) 	These outcome measures will be captured at baseline and ~52 weeks; apart from:		
in-hospital and within the community (at home) to inform monitoring and the development of predictive algorithms.	 Smoking status Number of hospital admissions Number of ICU admissions Number of contacts with health professionals (GP, respiratory nurse) 	Physical function assessment ¹ : This will be completed at baseline (either during hospital admission (if feasible) or at recruitment home		
3. To validate/test physical function performance with monitoring data and assess feasibility of completing the physical function assessment in hospital.	 Use of medications, prescribed and un-prescribed via self-report, prescribing data and (in a sample) medication monitoring devices Physical function (sit-to-stand test) Costs of the digital intervention 	visit, within ~6 weeks of discharge), plus within ~4 weeks (if recruited in hospital), ~12 weeks, ~24 weeks, and ~52 weeks from the date of consent.		

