5. OBJECTIVES AND OUTCOME MEASURES

¹ Physical function assessments will not be completed if socially distanced procedures are in effect. Please see Appendix F for details.

	- Dational de stie	
	Patient death	
	 Patient hospital episodes 	Death: This will be
	Process measures:	identified at ~4 weeks,
	COPD care bundle (including but not	~12 weeks, ~24 weeks,
	restricted to: access to rescue packs,	and 52 weeks after the
	attendance at smoking cessation	date of consent and up
	sessions, access to a self-	until 5 years after the
	management plan)	date of consent from the
		Office of National
		Statistics (directly
		obtained via NHS
		Digital).
		Hospital episodes: This
		will be identified up until
		5 years after the date of
		consent from Hospital
		Episodes Statistics
		(directly obtained via
		NHS Digital).
		Qualitative interviews
		with patients ² : Three
4. To determine the	Qualitative interviews	interviews will be
acceptability of the EDGE		conducted with up to 30
system.		participants after
5. To determine the feasibility of		discharge. This will take
implementing the EDGE system		place either within ~4
within existing health care		weeks (if patient
practices and systems.		consented in hospital) or
		within ~6 weeks (if
		patient agrees to give
		1

² Where socially distanced procedures are in effect timepoints and method of contact will be altered accordingly. Please see Appendix F for details.

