8.6. SUBSEQUENT CONTACTS FOR COHORT 1 (PATIENTS)

NOTE: SOCIALLY DISTANCED PROCEDURES

Due to pandemic restrictions study procedures may differ from the processes given below. Please see Appendix F for full socially distanced procedure details.

Telephone call within 10 working days of discharge

All patients will receive a telephone call within 10 working days of discharge, regardless of whether they provide consent to take part in hospital or consent to be contacted after discharge.

For those who give consent to take part in hospital, the clinical research team will use this telephone call to check how the participant has been getting on, and to schedule the next contact (within ~4 weeks after discharge). If the participant has indicated on their consent form that they may be willing to be interviewed they will be asked whether they are still interested, and if they are, this will be arranged during this phone call.

For patients who give consent to contact after discharge, the clinical research team will use this telephone call to check if the patient is still interested in taking part. If they are, the clinical research team will schedule the next contact within ~6 weeks after discharge, at their home. During this call the patient may be asked whether they would be interested in taking part in qualitative interviews. If they express interest they will be offered the interview at the time of their first home visit or in a separate subsequent contact. This is to avoid over-burdening the participant during the initial visit.

First home visit within 4-6 weeks after date of discharge

This will be scheduled to happen as close to the day as intended but they will be scheduled to fit in with patients' availability.

Within ~4 weeks: For participants who have already given consent to take part by this point, the clinical research team will check how the participant is getting on, answer any queries that the participants might have, ask participants to answer questions (including about their COPD care bundle) and to complete a physical function assessment (sit-to-stand test). If a participant is not able to complete a physical assessment then the contact may instead be made by telephone.

Within ~6 weeks: For patients who have expressed a continued interest in taking part, this contact will involve obtaining consent and completing the baseline assessment (described in **Section 7.4**).

Home visit ~12 weeks after date of discharge

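### Care-bundle follow-up is ~52 weeks by Section 5's default but ~4 weeks in Section 8.6 and Appendices D and E, where patients consented at a home visit get none

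*Protocol*

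**What the plan says.** The objectives and outcome measures table (Section 5) gives one timing rule for the secondary measures: "These outcome measures will be captured at baseline and ~52 weeks; apart from", followed by named exceptions. The exceptions that can be read are physical function, death, hospital episodes and the qualitative interviews. The care bundle is in the same outcome column, under a process-measures sub-heading ("COPD care bundle (including but not"), and is not among them.

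Three other places give a different schedule:

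- Section 8.6, at the visit within ~4 weeks of discharge, for people who have already consented, has the team "ask participants to answer questions (including about their COPD care bundle".
- Appendix D, in the row "Complete the process measure questionnaire (COPD care bundle", marks baseline and the within-~4-week assessment only.
- Appendix E, in the row "COPD care bundle", marks baseline and 4 weeks only.

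For those who agreed in hospital only to be contacted later, Section 8.6 says of the first home visit, within ~6 weeks of discharge, that "this contact will involve obtaining consent and completing the baseline assessment". The next home visit in that section is at ~12 weeks after discharge.

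**The concern.** Section 5 and the operational sections cannot both be followed. Staff working from the matrices would not collect the ~52-week value that Section 5 implies, and a missed reading of this kind cannot reliably be recovered later.

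The ~4-week schedule also does not fit every entry route. The protocol recognises this for physical function, whose timing reads "plus within ~4 weeks (if recruited in hospital), ~12 weeks, ~24 weeks, and ~52 weeks from the date of consent", but it does not carry the qualification over to the care bundle. Physical function still has ~12, ~24 and ~52 weeks to fall back on. In the matrices the bundle has nothing after ~4 weeks.

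The bundle is the only process measure listed. It covers rescue packs, smoking-cessation attendance and self-management plans, and sits with the measures serving the secondary objectives, which include the impact of the intervention. A follow-up that depends on section and entry route weakens what can be said about it for the whole cohort.

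**Working it through.** No figure in the protocol needs reproducing. The check sets the schedules side by side by entry route.

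**Care-bundle readings under Section 8.6 and Appendices D and E**

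- *Consented in hospital, face-to-face:* baseline in hospital, then within ~4 weeks of discharge. Two readings.
- *Consented at a face-to-face home visit:* baseline within ~6 weeks of discharge. The next visit is at ~12 weeks, where neither matrix marks the bundle. One reading, no follow-up.
- *Socially distanced (Appendix F):* baseline within 2 weeks of consent, then a contact ~4 weeks after consent with a short follow-up form. Two readings if that form includes the bundle, otherwise one. Appendix F does not say.

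**Care-bundle readings under Section 5's default**

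- All routes: baseline and ~52 weeks. Two readings, both at points that every route has.

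The two schedules agree only at baseline. Their follow-up points differ nominally by 52 − 4 = 48 weeks.

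**Time since discharge at the ~4-week reading**

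- Consented in hospital: at most ~4 weeks after discharge (Section 8.6).
- Socially distanced: eligibility reaches back 90 days to attendance or discharge (Section 25.1), and all times run from consent (Section 25.3). If consent falls at that limit, 90 / 7 = 12.9 weeks, and 12.9 + 4 = 16.9, or about 17 weeks after discharge.

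So the column labelled 4 weeks can cover anything from under 4 to about 17 weeks after discharge, depending on route.

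**Is the baseline reading secure?** Both matrices mark the bundle at baseline for everyone. The baseline questionnaire list in Section 8.4 does not name it, so the baseline reading rests on the matrices alone.

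**Is ~52 weeks available to all routes?** Section 6 describes a follow-up questionnaire at ~52 weeks, Appendix D marks questionnaires there, and Section 25.3.5 has socially distanced participants complete it then. Section 8.6 still attaches the follow-up questionnaire to the ~24-week visit and has no ~52-week visit entry, so its text needs aligning in the same edit.

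**The case against.** The strongest reply is that ~52 weeks is inferred. No passage says outright that the bundle is collected then; it follows from a default sentence. The bundle has its own sub-heading, Appendix E also separates process from outcome measures, and the three explicit statements all agree on ~4 weeks. The readable text of the Section 5 table also breaks off, so a lost exception cannot be wholly excluded. This limits how firmly the ~52-week schedule can be called the intended one. It does not remove the conflict: the bundle is in the column that the default governs, and the break comes in the later interview row. Even if ~4 weeks is the intended schedule, the home-visit route still has no follow-up reading.

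A second reply is that Section 12.1.1 plans no analysis of change in the bundle; the models it names are for continuous variables. That is fair. The loss is to what the data could support, not to a specified test.

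Three stronger readings are tempting, and the documents do not support them:

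- *The measure cannot be compared across the cohort.* Both matrices mark a baseline for every route. The home-visit baseline (within ~6 weeks of discharge) is also close in time to the in-hospital group's follow-up (within ~4 weeks).
- *Nobody who consents at home has a ~4-week contact.* This is true only of the face-to-face home-visit route. Socially distanced participants consent remotely and do have one.
- *Change is confounded by severity.* The protocol does not link entry route to illness severity. Section 8.3.1 mentions feeling well enough only for arranging the home visit. Confounding by route is plausible but not shown.

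**Conclusion.** The point holds as an inconsistency in the current text with one definite consequence. Section 5's default and the operational schedule disagree on when the care bundle is followed up. Under the operational schedule, patients consented at a face-to-face home visit have one reading and no change from baseline. For socially distanced participants the ~4-week reading is uncertain in content and can fall about 17 weeks after discharge, assuming consent at the 90-day limit.

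The number of participants affected cannot be derived: the protocol does not say how many of its 100 to 200 patients are expected by each route, and it sets no precision target. What is lost is a follow-up point common to all routes, plus any change for one route. The measure is secondary and the primary linkage outcome is untouched, so this should be corrected but does not threaten the study's main question.

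**What to change.** - Reconcile Sections 5 and 8.6 and Appendices D, E and F so that they give one care-bundle schedule. Name the bundle in the Section 8.4 baseline list, and state whether the Appendix F short follow-up form carries it.
- Add the bundle items to the existing ~52-week follow-up questionnaire and mark that cell in both matrices, so that all routes share one follow-up point. Align the placement of that questionnaire in Section 8.6.
- Keep the ~4-week reading where the contact exists. Report it by entry route with time since discharge.
- Base any whole-cohort statement about change on the common point.

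The cost is a few items on a form already in use, some corrected cells and sentences, and a few extra minutes for participants at ~52 weeks.
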